4.4 Subject Recruitment and Screening

Patients will be recruited from admissions at participating centers for suspected KD with IVIG administration. Families of Kawasaki Disease patients will be referred to the research team by physicians involved in patients care. In general, the Cardiology service is involved with KD patient's evaluation and care immediately after admission. Standard clinical care usually includes a screening or baseline echocardiogram. Patients will be screened for study suitability by the research staff. If the family shows interest in the study, they will undergo consent procedures, which will be conducted by the research team. The study will be described verbally to the patient and family. After the introduction and description of the study, the family will be given adequate time to read and review the written consent/ assent forms. Time will be allotted for questions and additional discussion if necessary. Family friends, relatives or additional support persons (at the request of the parent/guardian) may also be present to hear and read what is being asked of the patient/family.

Patients will be enrolled only after the necessary criteria for KD diagnosis has been documented in the medical record and serious infection as the source of fever has been reasonably eliminated. Patients will be screened prior to IVIG, but will not be enrolled until IVIG orders are written.

4.5 Early Withdrawal of Subjects

4.5.1 When and How to Withdraw Subjects

Subjects may be withdrawn from the study prior to the expected completion of that subject for health, logistical, or personal reasons (i.e. serious adverse events, failure of subject to adhere to protocol requirements, subject consent withdrawal, disease progression, etc). No safety consequences are anticipated with early withdrawal from the study since etanercept is adjunctive therapy.

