We will test the hypothesis that TNF- α antagonism with etanercept improves the clinical response to standard of care treatment with IVIG and aspirin therapy in KD patients between 2 months and 20 years of age. To test this hypothesis we will perform a double-blinded placebo controlled trial in 196 children with KD and obtain data in order to achieve an orphan designation for etanercept.

Primary Aim

1. Determine if etanercept (0.8 mg/kg, maximum 50 mg) given subcutaneously reduces IVIG refractory rate and retreatment rate in the KD patient population. Our goal is to randomize and complete the trial in 110 patients in the etanercept treatment group and 110 patients in the placebo group.

Secondary Aims

1. Determine if the safety profile differs between the etanercept treated group and the placebo group.
2. Determine if etanercept treatment alters the rate of coronary artery dilation and disease (CAD) defined by z-scores at 2 and 6 weeks after treatment.
3. Determine the pharmacokinetics of etanercept in KD patients

3 Research Design and Methods

We propose a placebo-controlled randomized double blind multi-center study in patients, age 2 months to 20 years, with acute Kawasaki disease. All study investigators will be blinded except for pharmacists.

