4.5.2 Data Collection and Follow-up for Withdrawn Subjects

Follow-up calls will be made to the patient's family upon early withdrawal from the study.

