6.5 Visit 5 (Day 44 ± 4 days)- Clinic

A physical exam and a blood draw (approximately 7 cc) are required. . The blood sample is sent to the laboratory for the tests listed in schema. An Echo/ EKG is performed. No study drug is administered.

6.6 Treatment for refractoriness to IVIG.

All patients who fit the requirements for refractoriness to IVIG (see section 3.1) will receive standard clinical treatment as determined by the attending physician. Standard treatment is usually a second dose of IVIG, and is defined in the American Heart Association guidelines. Retreatment with IVIG will not interrupt the study and study medication should still be administered.

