The pharmacist and pharmacy technical staff will be not be blinded. The study statistician will provide each site pharmacy with randomization table. Pharmacists will supply each patient with drug or placebo, both provided by Amgen in separate labeled vials. Pharmacists will draw dose in syringes and dispense to nursing for administration. Drug accountability will be monitored by the CRO as described below. Study randomization codes and links to patients will be kept in secure records in pharmacy. All other study personnel involved in administration of drug will be blinded.

6.9 **IVIG Retreatment**

As noted in section 3.1: The primary aim of this study is to determine if Etanercept (Enbrel) 0.8 mg/kg given subcutaneously to patients with acute Kawasaki Disease will reduce the incidence of IVIG refractoriness as defined in the joint American Heart Association and American Academy of Pediatrics Endorsed Clinical Report: "Refractory Kawasaki Disease will be defined as the persistence or recrudescence of fever ($\geq 38.0^{\circ}\text{C}$ or 100.4°F) at least 36 hours after the end of the IVIG infusion"³. Persistent or recrudescent fever is the sole criteria for determining the need for retreatment. The clinical decision can be supported by persistent symptoms and persistent elevation or rebound of inflammatory parameters such as CRP. The protocol requires waiting at least 36 hours after completing the first IVIG dose before initiating the second dose.

7 Statistical Design and Analysis

The primary outcome variable is the Y/N determination of whether the subject is refractory to IVIG treatment, defined as persistence of fever $>38^{\circ}\text{C}$ beyond 36 hours from completion of IVIG treatment, or recurrence of fever within 10 days, and clinical decision to retreat with IVIG. Chi-square testing will be used to compare the proportions of subjects classified as refractory to IVIG treatment between the group randomized to receive Etanercept as an adjunctive therapy and the group randomized to receive placebo. If necessary (due to low cell counts), a Fisher's Exact test can be substituted. Stratified versions of the chi-square and Fisher's tests are available in StatXact (Cytel Incorporated) to allow stratification by center.

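### Section 4.5 lets children leave the study, not only study drug, for reasons that can relate to outcome, and then requires only unspecified calls, so day-10 status and the later echocardiograms can be lost selectively.

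*Combined protocol and SAP*

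**What the plan says.** Section 4.5.1: "Subjects may be withdrawn from the study prior to the expected completion of that subject for health, logistical, or personal reasons". The examples given are "serious adverse events, failure of subject to adhere to protocol requirements, subject consent withdrawal, disease progression, etc". What ends is participation in the study; stopping study drug while staying in follow-up is not offered as a separate status.

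Section 4.5.2 is a single sentence: "Follow-up calls will be made to the patient's family upon early withdrawal from the study". It gives no content, number, timing or duration for the calls, and no outcome that they must establish.

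Section 7 defines the primary outcome as persistent fever beyond 36 hours, or "recurrence of fever within 10 days, and clinical decision to retreat with IVIG". For the test, "Chi-square testing will be used to compare the proportions of subjects classified as refractory to IVIG treatment", comparing the two groups as randomised. It gives no rule for a child whose status is unknown and no sensitivity analysis.

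Two other places bear on the point. Section 6.6 (treatment for refractoriness) says: "Retreatment with IVIG will not interrupt the study and study medication should still be administered". Section 8.1 (Expected Adverse Events) names readmission for recurrent or persistent fever as an expected serious adverse event.

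**The concern.** After discharge, fever is captured through a two-week temperature log kept by the parents (Sections 6 and 6.1). The log is not said to continue after withdrawal. The coronary endpoints need echocardiograms at days 14 and 44, which a call cannot supply. A child withdrawn early can therefore have no day-10 status and no later coronary measurement.

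If such losses had nothing to do with outcome, they would cost only a little power. The listed reasons make that hard to assume. Disease progression and serious adverse events can both sit close to treatment failure, and the plan itself treats a difference in safety between the arms as an open question (Section 2, first secondary aim). Loss that depends on outcome and differs between arms biases the primary comparison. It also removes coronary data, possibly from the children at highest coronary risk. Outcomes that were not collected at the time may not be recoverable later.

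**Working it through.** **Figures in the plan.** The plan gives no withdrawal rate and no dropout allowance, so it has no figure of its own to reproduce on this point. The sample-size row in Section 4.3 (0.25 versus 0.08, 97 per group) serves here only to fix the design effect. Its stated 80% power does not reproduce, but that is a separate matter and does not enter below.

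**Which children can be lost.** Set Sections 4.5, 6.6, 7 and 8.1 side by side:

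1. A child with fever who has already been retreated is a recorded failure. Section 6.6 keeps that child in the study. If the child later leaves, the primary outcome stands and only the remaining echocardiograms are lost.
2. A child who leaves for a serious adverse event, progression or non-adherence before day 10, with no retreatment decision yet, has no primary outcome unless the calls happen to obtain it. Section 6.6 does not cover this child.
3. A child who leaves after day 10 has a primary outcome but may lack one or both echocardiograms.

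The primary comparison is exposed through group 2 only. The coronary endpoints are exposed through all three.

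**Illustration.** Inputs: 196 children allocated 1:1, so 98 per arm (Sections 4 and 4.3); uncorrected Pearson test (Section 7 does not specify a correction); two-sided 5% level (assumed, as none is stated). The numbers lost are assumptions.

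z = (pC − pE) / √[p̄(1 − p̄)(1/nE + 1/nC)], where p̄ is the pooled proportion.

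- Full data, borderline result: 15/98 = 0.1531 and 25/98 = 0.2551; p̄ = 40/196 = 0.2041; SE = 0.0576; z = 0.1020/0.0576 = 1.77; p = 0.076.
- Three etanercept failures unrecorded: 12/95 = 0.1263; p̄ = 37/193 = 0.1917; SE = 0.0567; z = 0.1288/0.0567 = 2.27; p = 0.023.

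The crossing does not depend on the test: Fisher's exact p goes from 0.110 to 0.028, and the continuity-corrected p from 0.111 to 0.037.

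| Scenario (etanercept vs placebo) | Full data | After loss |
|---|---|---|
| Borderline, 3 etanercept failures lost | 15/98 vs 25/98, p = 0.076 | 12/95 vs 25/98, p = 0.023 |
| Borderline, 2 placebo failures lost | 13/98 vs 25/98, p = 0.030 | 13/98 vs 23/96, p = 0.055 |
| Borderline, 3 failures lost in each arm | 15/98 vs 25/98, p = 0.076 | 12/95 vs 22/95, p = 0.058 |
| Near design effect, 3 etanercept failures lost | 8/98 vs 25/98, p = 0.001 | 5/95 vs 25/98, p = 0.0001 |
| Near design effect, 3 placebo failures lost | 8/98 vs 25/98, p = 0.001 | 8/98 vs 22/95, p = 0.004 |

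**False-positive rate.** Let the true rate be 25% in both arms, and let a share f of refractory children be lost from the etanercept arm only. The observed etanercept rate becomes 0.25(1 − f)/(1 − 0.25f) on 98(1 − 0.25f) children. The two-sided rejection rate is Φ[(d − 1.96·se0)/se1] + Φ[(−d − 1.96·se0)/se1], where d is the observed difference, se0 its pooled and se1 its unpooled standard error.

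- f = 10% (about 2.5 children): observed rate 0.231, rejection rate 6.1%.
- f = 20% (about 5 children): observed rate 0.211, rejection rate 9.9%.
- f = 30% (about 7 children): observed rate 0.189, rejection rate 17.0%.
- The same share (20%) lost in both arms: 5.0%.

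**Loss unrelated to outcome.** Losing 10% at random from 98 per arm leaves 88. Power for 0.25 versus 0.08 is then 87% uncorrected or 82% corrected, against 90% or 86% with no loss. That is a minor cost.

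**The case against.** The strongest reply is that the plan protects most failures already, and much of it stands.

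- Section 7 compares the groups as randomised and nowhere excludes withdrawn children. A reader might infer a completers comparison from the Primary Aim: "Our goal is to randomize and complete the trial in 110 patients in the etanercept treatment group". That sentence is an enrolment goal, not an analysis set, and no completers analysis is planned.
- A reader might infer that withdrawal removes failures already observed. Nothing supports this. Section 9.1 keeps information collected before authorisation is revoked, and a child already classed as refractory stays so.
- A reader might infer that Sections 4.5.1 and 6.6 flatly contradict each other. They do not: 4.5.1 is permissive and does not define disease progression as IVIG refractoriness, while 6.6 is the specific text for refractory children and mainly limits the problem. But 6.6 is silent on leaving for a serious adverse event, progression or non-adherence, so the two sections still have to be reconciled.
- Calls could establish fever and retreatment. Unresolved adverse events are followed to resolution (Section 8.1), and an IVIG retreatment form exists (Attachment 3). True, but no text requires day-10 refractory status to be obtained for a withdrawn child.
- Section 8.1 leaves the precise definition of a serious adverse event for readmissions to the DMC Organizational Meeting, so how often this route would open is uncertain.
- The shift in p needs a borderline result and losses that are all failures in one arm of a double-blind trial. That is correct, and it is why the figures are only illustrations.

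**Conclusion.** The point holds as a weakness in a stated rule. Following Section 4.5 as written can lose the primary outcome of children who leave before it is known, and can lose coronary data from any child who leaves before day 44, for reasons that may relate to outcome. It goes beyond an absent intention-to-treat statement, because analysing children as randomised cannot supply an outcome that nobody collected.

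The size is unknown, since the documents give no withdrawal rate. Two or three unrecorded failures in one arm can move a borderline result across 5% in either direction. Near the planned effect they do not change the conclusion, and an equal share lost in both arms under no effect leaves the false-positive rate at 5%. A reader might infer that the primary result is likely to be biased; the documents support only that it could be, through differential loss before day 10. This is a change that should be made, at low cost.

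**What to change.** - **Section 4.5.1:** separate stopping study drug from leaving follow-up. State that a child who stops drug for any reason, including a serious adverse event, progression or non-adherence, stays in follow-up unless consent is withdrawn. Reconcile the wording with Section 6.6. The decision to stop study drug stays with the clinicians.
- **Section 4.5.2:** say what is collected: fever and IVIG-retreatment status to day 10, by call or from records, and the day-14 and day-44 echocardiograms.
- **Section 7:** analyse all randomised children by assigned arm. Add a sensitivity analysis that counts a child without day-10 status as refractory, and report the number of such children by arm. In the first illustration, this returns 12/95 to 15/98 and p to 0.076. The rule is not conservative in every case: where the missing children are on placebo it favours etanercept, which is why the counts by arm matter.

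Cost: protocol wording, plus some record retrieval and follow-up effort. Forms for temperature, retreatment and echocardiography already exist. The documents do not say that every follow-up echocardiogram is routine care, so some may need extra arranging. Label: cheap improvement.

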4.5.2 Data Collection and Follow-up for Withdrawn Subjects

Follow-up calls will be made to the patient's family upon early withdrawal from the study.

4.5.3 Emergency Blind Breaking

At the beginning of the study each site will be instructed on the method for emergency blind-breaking. Blinding codes should be broken in emergency situations only if this is required for proper treatment. The

primary investigator at the site will contact [name] to assess the necessity for un-blinding. In the unlikely event that [name] is unreachable; the primary investigator will be responsible for making the decision to un-blind the patient.

The study investigator will instruct the participating site pharmacy to break the blind to the treating physician only. The study investigators at the site as well as [name] are to remain blinded to protect the integrity of the data.

5 Study Drug

5.1 Description

Etanercept is a recombinant TNF receptor Fc Fusion protein. It is pharmacologically classified as a TNF antagonist, with the sole active ingredient being etanercept.

Etanercept powder is to be reconstituted with sterile diluent supplied by Amgen, Inc. prior to its subcutaneous injection such that the final dosage achieved is 0.8 mg/kg. Each vial of powdered etanercept contains 25 mg etanercept, 40 mg mannitol, 10 mg sucrose, and 1.2 mg tromethamine.

5.2 Treatment Regimen

Subjects will be given subcutaneous injections of 0.8 mg/kg etanercept 3 times at weekly intervals, starting at initial diagnosis.

5.3 Preparation and Administration of Study Drug

Participating Hospital's Investigational Pharmacy will prepare the study drug according to the manufacturer and research protocol's directions. Amgen will provide study drug and placebo to each site's pharmacy. Etanercept will be reconstituted aseptically with the Amgen-supplied Sterile Bacteriostatic water for Injection, USP (0.9% benzyl alcohol) so that the desired study dosage is met. Following drug preparation, the Investigational Pharmacy will dispense the study drug to the study investigators so that it may be administered to the patient.

5.4 Subject Compliance Monitoring

The study coordinator will track subject compliance with the study treatment regimen. Subjects non-compliant with the study treatment regimen will be contacted to so that conflicts which may be hindering their compliance may be resolved.

5.5 Prior and Concomitant Therapy

The following medical therapies are not permitted for study participation:

- Treatment with any TNF α antagonist or steroid within 48 hours prior to initiation of IVIG
- Current use of an investigational device or drug trial(s), or receipt of other investigational agent(s) within 28 days of baseline visit
- Prior or concurrent cyclophosphamide therapy
- Concurrent sulfasalazine therapy
- Concurrent isonicotinic acid hydrazide therapy
- Any live vaccine 30 days prior to, or during the study. Patient may be enrolled in the study 14 days after administration of Influenza mist vaccine.
- Prior (within 3 months preceding enrollment) or concurrent use of immunosuppressive agents

In addition, any medical therapies that may cause harm to the patient, as judged by the patient's physician on a case-by-case basis, will not be permitted.

CONFIDENTIAL

This material is the property of the Seattle Children's Research Institute. Do not disclose or use except as authorized in writing by the study sponsor-investigator.

IVIG (2 g/kg) and aspirin (80-100mg/kg Q6 hr until afebrile then 3-5 mg/kg/day) are standard treatment regiments for acute Kawasaki Disease, their concomitant therapy is to be expected and permitted.

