Efficacy of current treatment: The joint statement of the American Heart Association and the American Academy of Pediatrics states emphatically that “the efficacy of IVIG administered in the acute phase of Kawasaki disease in reducing the prevalence of coronary artery abnormalities is well established.”³ The first major controlled randomized trials in KD patients in the United States (1986) showed superior prevention of coronary artery disease in children with acute KD by IVIG and ASA versus ASA alone⁸. Subsequently, Newburger et al showed that a single high dose of IVIG (2g/kg) administered over 10 hours reduced the

CONFIDENTIAL

This material is the property of the Seattle Children's Research Institute. Do not disclose or use except as authorized in writing by the study sponsor-investigator.

prevalence of coronary abnormalities compared to daily infusions of 400 mg per kilogram for four consecutive days. Both groups also received ASA (100 mg per kilogram per day) for 14 days¹². Accordingly, AHA/AAP guidelines recommend IVIG 2g/kg in a single dose with some modifications in ASA dosing. In Japan, where prevalence of KD is substantially higher than in the U.S., IVIG is usually given two separate 1g/kg doses on consecutive days¹³.

Although the historical studies show that IVIG prevents coronary artery dilation^{8, 12}, the failure rate of this nonspecific treatment for KD remains high¹⁴. It is difficult to determine current IVIG efficacy, as criteria and technological advances have altered for reporting coronary artery disease (CAD), and we could not ethically perform a randomized placebo trial excluding affected patients from receiving IVIG. Discrepancies exist between rates of IVIG failure reported from Japan and the United States^{13, 14}. These differences are partially due to methodology in defining coronary artery dilation. The discrepancies create challenges in interpretation and performing comparisons of clinical trials, as well as evaluation of new adjunctive therapies. For instance, Inoue et al reported that only 3.4% of patients had CAD by 1 month after receiving the standard Japanese IVIG regimen¹³, while the most recent U.S. multicenter trial reported 18.9% CAD in all patients at 6 weeks, and 9% for patients without CAD at baseline¹⁴.

[figure not shown]

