 - l. Severe comorbidities (diabetes mellitus requiring insulin, CHF of any severity, MI, CVA or TIA within 3 months of screening visit, unstable angina pectoris, uncontrolled hypertension (sitting systolic BP > 160 or diastolic BP \geq 100 mm Hg), oxygen-dependent severe pulmonary disease, history of cancer within 5 years [other than resected cutaneous basal or squamous cell carcinoma or in situ cervical cancer])
 - m. Exposure to hepatitis B or hepatitis C or high risk factors such as intravenous drug abuse in patient's mother, or history of jaundice (other than neonatal jaundice).* SLE, history of multiple sclerosis, transverse myelitis, optic neuritis or chronic seizure disorder.

CONFIDENTIAL

This material is the property of the Seattle Children's Research Institute. Do not disclose or use except as authorized in writing by the study sponsor-investigator.

- n. Use of a live vaccine (Measles Mumps Rubella or Varicella) 30 days prior to or during this study with the exception that a patient who has received Influenza mist vaccine may be enrolled after 14d from administration of the vaccine.
- o. Any condition judged by the investigator to cause this clinical trial to be detrimental to the patient
- p. History of non-compliance with other therapies
- q. Must not have received immunosuppressive agents for at least three months prior to enrollment.

*Note, liver enzymes, AST or ALT are frequently elevated in KD, and will not be used as an exclusion.

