6.1 Visit 1 - Hospital

The patient is admitted into the hospital. Patient family is referred to the research staff for study discussion and consent. The patient is screened for eligibility, study discussion is conducted, and consent is obtained. Assent will also be obtained if deemed required by IRB. (see section entitled "Protection of Human Subjects").

All patients will receive standard treatment for KD as stated in the AHA-AAP guidelines. This includes IVIG 2 gm/kg over 10 hours or longer if interruptions occur in the infusion and high dose ASA, administered at 80 to 100 mg/kg per day in 4 doses until patients have been afebrile for 48 hours. Subsequently, patients will continue low dose ASA 3-5 mg/kg per day until 6 weeks or longer at the discretion of the treating Pediatric Cardiologist.

The blood for the baseline measurements can be drawn with the IV start or from the IV line. Labs obtained upon hospital admission will be used for baseline data. The PK blood sample will be processed and stored for later shipping by the lab or study personnel, while the other blood samples shown in study schema are sent to the central hospital laboratory for processing and results. An Echo and EKG are performed. A nurse administers a subcutaneous injection of study drug or equivalent volume of placebo at the appropriate dosage 0.8 mg/kg (maximum 50 mg). Etanercept must be administered within 48 hours after initiating IVIG therapy, and as early as possible. Etanercept should not be given prior to starting IVIG infusion. After discharge, the parents of the patient are to record daily temperatures between 4PM and 6PM for the next two weeks in a log provided by the nurse coordinator. Thermometer will be given to family if not already available or provided by hospital and coordinator will instruct patients regarding the proper procedure for taking and recording temperature. If the parents believe that their child has a fever, they are to record the child's temperature regardless of the time of day and notify the study coordinator if temperature is $> 38.0^{\circ}\text{C}$. If the study coordinator is unavailable the family should call the on-call cardiologist. If the child is readmitted, an extra study visit will occur within 12-24 hours of the patient being readmitted, and a physical exam, CBC, CRP, ESR, ECG, and Echo will be completed. Parents are to notify the study coordinator if they find any signs of infection in the patient.

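### Sections 5.5 and 6.1 state the aspirin dose and the switch to low dose differently, and the tuberculosis note in Section 4.2 conflicts with the rescue permitted in Section 6

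*Combined protocol and SAP*

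**What the plan says.** **Aspirin.** Section 5.5 (Prior and Concomitant Therapy) describes the background regimen as "aspirin (80-100mg/kg Q6 hr until afebrile then 3-5 mg/kg/day) are standard treatment regiments". Section 6.1 (Visit 1) opens its treatment paragraph with "All patients will receive standard treatment for KD as stated in the AHA-AAP guidelines" and then has high-dose aspirin "administered at 80 to 100 mg/kg per day in 4 doses until patients have been afebrile for 48 hours". Both sections give the same low dose, 3-5 mg/kg per day. Section 6.1 continues it to 6 weeks or longer; Section 5.5 gives no duration.

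**Immunosuppression.** Section 5.5 has a list headed "The following medical therapies are not permitted for study participation". One entry is "Prior (within 3 months preceding enrollment) or concurrent use of immunosuppressive agents". A separate entry covers any TNF "antagonist or steroid within 48 hours prior to initiation of IVIG". Section 4.2 repeats the 48-hour rule as item e and has, as item q, "Must not have received immunosuppressive agents for at least three months prior to enrollment". The note on PPD testing at the end of Section 4.2 says that the cohort will be given no immunosuppressive drug besides etanercept. The text of Section 6 just before 6.1 permits high-dose steroids and/or infliximab during the study for recurrent disease, on Rheumatology's recommendation.

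**The concern.** Sections 5.5 and 6.1 are both current text, and they express a paediatric aspirin dose in different units with a different rule for stepping down. A site that works from Section 5.5 alone could arrive at a different daily total and a different switch time from a site that works from Section 6.1. Section 1.1 distinguishes an anti-inflammatory action of aspirin at high doses from an antiplatelet action at low doses, so by the protocol's own account the switch point has substance.

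The second issue is one of accuracy. The PPD note names additional immunosuppression as a risk factor for tuberculosis and uses its absence as one reason for not testing. Section 6 allows the treatment that the note says will not occur. What is at stake is dosing clarity and the correctness of a safety rationale.

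**Working it through.** **Step 1: daily high-dose aspirin.** Inputs: 80-100 mg/kg with a 6-hour interval (Section 5.5); 80-100 mg/kg per day in 4 doses (Section 6.1).

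- Doses per day at a 6-hour interval: 24 / 6 = 4.
- Section 5.5 read as an amount per dose: 4 x 80 = 320 and 4 x 100 = 400 mg/kg/day.
- Section 6.1: 80-100 mg/kg/day, that is 80 / 4 = 20 to 100 / 4 = 25 mg/kg per dose.
- Ratio: 320 / 80 = 400 / 100 = 4.
- Section 5.5 read as a daily total divided every 6 hours: 80-100 against 80-100 mg/kg/day, difference 0.

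The text of Section 5.5 does not choose between the readings. In the same sentence it writes a per-day unit for the low dose and none for the high dose, which points to the per-dose reading. The number range and the four daily doses match Section 6.1, which points to the daily-total reading. The only other high-dose figure, in Section 1.1, is "Both groups also received ASA (100 mg per kilogram per day) for 14 days". That is the regimen of a cited trial, and the next sentence says that the guidelines modify aspirin dosing somewhat, so it does not settle what Section 5.5 means.

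**Step 2: the switch rule.** Section 5.5 ends high dose when the child is afebrile, with no duration. Section 6.1 requires 48 afebrile hours.

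- If the Section 5.5 wording abbreviates the Section 6.1 rule, the gap is 0.
- If it means the first afebrile point and fever does not return, the gap is 48 hours.
- If fever returns, the 48-hour clock restarts and the gap grows. Illustration with assumed times: afebrile at hour 10, febrile at hour 30, afebrile from hour 50. Section 5.5 switches at hour 10, Section 6.1 at 50 + 48 = 98, a gap of 98 - 10 = 88 hours.

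So 48 hours is not an upper bound. Recrudescent fever is part of the Section 3.1 endpoint definition, so the third case is one that the protocol itself expects.

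**Step 3: the PPD note against permitted rescue.** The note says that no other immunosuppressive drug will be given, and in reporting the literature it speaks of immunosuppressive agents other than etanercept, so it counts a TNF antagonist as one. Infliximab is also a TNF antagonist (Section 1.1). A patient given infliximab rescue under Section 6 would therefore fall outside the note's statement. Neither passage refers to the other.

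**Step 4: scope of the Section 5.5 bar.** For a narrow scope: steroids and TNF antagonists have their own 48-hour entry, which would be largely redundant if the three-month entry covered them, and the list heading can be read as governing entry only. For a broad scope: the entry says concurrent, the section title includes concomitant therapy, and the live-vaccine entry in the same list applies during the study. No passage defines the term, so this is missing detail and not a contradiction.

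**The case against.** The strongest reply is that Section 5.5 only describes what is expected and permitted, whereas Section 6.1 carries the instruction, so sites would work from Section 6.1. That difference in function is real and limits the practical risk. It does not remove the mismatch, because both are current protocol text and neither defers to the other.

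A reader might infer that Section 5.5 prescribes four times the Section 6.1 dose. The documents do not support that: the factor of 4 depends on a per-dose reading that the text does not state.

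A reader might also infer that steroid or infliximab rescue breaches Section 5.5, or that prior steroid use faces two conflicting windows. Neither follows. The bar is undefined in scope, the separate 48-hour entry weighs against applying it to these drugs, and Section 6 expressly answers whether rescue is permitted. Section 6 also says that it does not specify concomitant medications; if the Section 5.5 list governs entry only, the two largely coexist.

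Finally, a reader might conclude that omitting PPD testing loses its basis. It does not. The note is a cohort-level rationale that also rests on the short course, low local incidence, the delay that testing would cause, possible false negatives and exclusion by history. Those supports are untouched.

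**Conclusion.** The aspirin mismatch stands and carries the point: a factor of 4 in the daily high dose if Section 5.5 is read literally and 0 if it is a daily total, with the text silent on which. The switch wording differs on either reading of the dose, by anything from 0 to more than 48 hours, depending on what afebrile means in Section 5.5 and whether fever returns. The conflict between the PPD note and the rescue permitted in Section 6 also stands, as an inaccurate statement for any patient who receives that rescue; the documents give no rescue rate, so no patient count can be offered. The undefined scope of immunosuppressive agents in Sections 5.5 and 4.2 item q is minor.

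A reader might infer an effect on the primary endpoint, power or sample size. None is claimed: no sample-size input depends on these passages, and the documents give no figure from which an effect could be computed.

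**What to change.** - Reconcile Sections 5.5 and 6.1 so that one aspirin expression, with its unit, and one switch rule appear.
- Reconcile the PPD note in Section 4.2 and the list in Section 5.5 with the rescue paragraph in Section 6. State whether immunosuppressive agents in Section 5.5 and Section 4.2 item q includes steroids and TNF antagonists, and whether the concurrent-use entry applies to on-study rescue.

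The sponsor's clinicians decide which text stands. The cost is a protocol wording amendment, with no change to data collection or patient numbers.
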